The VA provides screening, surveillance and diagnostic colonoscopies, but many eligible male and female Veterans (8.8%) (14) to 10.5% (15) are underserved. Since sedation is standard (with escort requirement and Veterans' lack of knowledge of the unsedated option), without escort, these eligible Veterans do not participate (15). For example, in an unpublished recent (Aug to Dec 2015) audit, 51 female Veterans at VAGLAHS were scheduled, 30 completed with sedation, 21 cancelled or were no shows, and 6 were due to lack of escorts on the day of the appointed sedated colonoscopy. Based on CPRS records. none was offered the option of scheduled unsedated colonoscopy during the scheduling process. In another set of PI's unpublished pilot data 23% of female Veterans, and in a set of PI's published observations 33% male Veterans (5) were willing to participate in scheduled unsedated colonoscopy when the option was made available. Historically, 2% of Veterans without escort were offered unscheduled unsedated colonoscopy (6,14-22). Other Veterans prefer to avoid sedation, due to their post-traumatic stress disorders (e.g., unpleasant flashbacks triggered by sedation), or because of personal preference (e.g., watch the examination, no escort needed, save time with no recovery or activity restrictions). They request unsedated colonoscopy (23,24,13). Programs negatively affected by nursing shortage (20,21) and no shows due to no escorts (15) found an effective solution in offering the scheduled unsedated option (15,20,21). Scheduled unsedated colonoscopy permitted completion of colonoscopy in Veterans who had prior paradoxical agitation, or a history of narcotic drug use (25). An increasing number of VA (6,14-22) and non-VA (26,27) sites have reported unsedated colonoscopy in both male and female patients. Pain which can lead to termination of insertion indicates development of the least painful insertion technique is relevant to Veterans health (24). Water exchange (WE) is less painful (mild pain) than air insufflation (moderate pain) in the unsedated Veterans in studies with a predominance of male Veterans (5,6,22). The Pl's international collaborators demonstrated in RCTs that female had significantly higher insertion pain scores than male subjects, WE significantly reduced insertion pain in both gender, and WE was the least painful insertion method in both males and females (4). An even less painful method (converting mild to no pain in males, and moderate to mild in females) than WE in unsedated colonoscopy will further ensure its success in a patient-centered manner (8,9,23,24,25). The costs, nursing staff for recovery and VA-sponsored transportation, can be obviated. Completion for those with a personal preference for no sedation can also be accomplished effectively. The immediate aim (investigators with varying levels of experience in WE, cap and unsedated patients at multiple sites) is to assess the generalizability of the impact of WE plus cap (WECAC), as a potentially less painful insertion technique than WE. The primary outcome of RTMIP (unblinded measure, but one on which clinical decision is made) will be compared. Power estimates show the revised male and female sample size will permit significant differences to be demonstrated in some of the previously listed secondary outcomes. The non significant ones will be dropped. Record of these will be kept, however, to demonstrate comparability of the two groups. Furthermore, when the male and female data are combined, the sample size may reveal differences between WE and WECAC worth pursuing, thus providing pilot data for future studies (e.g. overall and segmental adenoma detection rates in scheduled unsedated Veterans). Informed/educated male and female Veterans who choose scheduled unsedated colonoscopy due to no escort or personal preference for no sedation will be considered for enrollment.

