D	WE	36/14/0	8	34%	26	40%	1.5 (0.7)		19 (11)
Fı	Frequency count; (%), % of total; mean (SD); L, liters; blank cell=data not listed in reports.								

Table 7 shows that indications were variable. WECAC required 1-2 L infusion; equivalent volume suctioned upon cecal arrival, confirming infused water suctioned mostly during insertion. Position change (25% vs. 34%) and abdominal pressure (37% vs. 40%) were needed less often with WECAC than in WE.

4. VA Palo Alto Healthcare System (Participant - [name] and others)

In 229 male Veterans successful minimal-sedation was 51% (water immersion) vs. 28% (air), P=0.0004, less pain (4.1±2.7 vs. 5.3±2.7; P=0.001) (56). Pl's coaching (42) led [name] to use WE (57). After coaching (42) co-investigator [name] has adopted WE (no formal published data).

(e) Significant correlation between RTMIP and recalled maximum insertion pain (PD/PI, [name])

The PI (5) and collaborators (3,4) have reproducibly confirmed that RTMIP (unblinded) is uniformly higher than recalled maximum insertion pain (blinded) and the 2 measures are significantly correlated (26).

(4) Work Proposed

(a) Study type descriptor. Prospective, multisite, multi-investigator, RCT, single (patient) blinded. Sites (no. investigators). VA: VAGLAHS (n=3); VAPAHCS (n=2); VANCHCS (n=2).

(b) Research design, methods and procedures to be used to accomplish the specific aims.

The investigators will describe the study at local lectures. The research coordinators will distribute flyers about the RCT to practitioners in primary care clinics, and will work closely with the colonoscopy schedulers to identify potential candidates (no escort, preference for no sedation). For scheduled unsedated Veterans, the coordinator will send each patient material (e.g. summary description, consent form) related to the RCT, with a follow up phone call to address questions that the Veterans may have. At all sites, Women's Health Clinics will assist the coordinators, to inform female Veterans of the scheduled unsedated option.

Inclusion criteria. *Informed/educated (about pros and cons of the unsedated option)* male and female *Veterans* (18-80 years old) undergoing diagnostic (positive stool occult blood test in the context of screening), surveillance (follow up of polyps) or screening (first-time) colonoscopy at participating sites, choosing scheduled unsedated colonoscopy for any reason (lack of escort, personal preference).

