Exclusion criteria. Decline to be randomized, unable to give consent or respond to questionnaires, history of colon surgery, active inflammatory bowel disease, lower gastrointestinal bleeding (except for occult blood or FIT positive in the context of colon cancer screening), therapeutic colonoscopy (e.g., hemostasis, removal of large polyp), proctosigmoidoscopy, bidirectional endoscopy, inadequate consumption of bowel preparation, known history of severe diverticulosis or diverticulitis, history of abdominal surgery previously requiring sedation for colonoscopy, current narcotic/anxiolytic medication use, prior unsuccessful experience with unsedated colonoscopy, emergent colonoscopy, evidence of colonic obstruction based on pre-colonoscopy clinical evaluation, current participation in other studies, medical condition that could increase the risk associated with colonoscopy (e.g., active cardiac or pulmonary disease or other serious disease), medical condition that would preclude a benefit from colonoscopic screening (e.g., cancer or any terminal illness), prosthetic heart valve, anticoagulant therapy, nonmedical problems (e.g., psychiatric disorders, excessive use of alcohol), need for special precautions in performing colonoscopy (e.g. antibiotic prophylaxis), and request of on demand sedation.

Primary outcome measure (for male and female subjects).

	_
Real time maximum insertion	_
pain (RTMIP) (unblinded) score	
(validation by correlation with	
recalled pain described below)	

Pain during insertion reported to the unblinded assisting nurse, visual analogue scale, VAS: 0=none, 10=most severe. The highest pain score will be tabulated for analysis. Timing of data collection will be at the discretion of the nurse to minimize bias by colonoscopist behavior.

Secondary outcome measures (for male and female subjects).

Proportion with no insertion pain Proportion report no pain during insertion of the colonoscope. Quality marker.

Insertion time	Time to cecum (clock display on monitor). Faster insertion is a quality marker
Proximal colon ADR	ADR from cecum to splenic flexure. Measure of high quality colonoscopy

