Primary outcome. Patient with insertion pain that cannot be brought to a tolerable level by colonoscopist implemented maneuvers will be considered failure of cecal intubation and the insertion will be discontinued. The pain level at the time of discontinuation will be noted for analysis.

Standardized validated instruments.

Proportion with no insertion pain, insertion time, proximal colon ADR (secondary outcomes in males) have been defined above; demographic data, co-morbidities, prior history and additional procedure based and patient level parameters will be analyzed as covariables (Tables 9 and 10).

Table 9: Demographic variables, co-morbidities and prior history				
Age	In years		Hemorrhoids	0=no, 1=yes
Gender	Male, female		Chronic pain treatments	0=no, 1=yes

Education	Elementary, high, college, graduate	Substance abuse	0=no, 1=yes
Ethnicity	White, Black, Hispanic, Asian, other	Prior abdominal surgery	0=no, 1=Yes (type)
BMI	Weight/height ²	Prior sedation colonoscopy	0=no, 1=yes
Indication	Screening, surveillance, diagnostic, pain	Prior unsedated colonoscopy	0=no, 1=yes

Table 10: Additional procedure based and patient level covariates				
Recalled maximum insertion pain	Maximum pain during insertion reported to a blinded observer after			
score (blinded data)	colonoscopy before discharge, VAS: 0=none, 10=most severe. Correlation with RTMIP.			
Overall ADR - entire colon	Proportion of patients with at least one adenoma of any size.			
Right colon ADR	ADR from cecum to hepatic flexure			
Adequacy of patient blinding	Patient guesses which method is used (<60% correct=adequate).			
Successful cecal intubation	0=no, 1=yes			
Successful cecal ilitubation	Abdominal pain prior to start of colonoscopy: 0, none to 3, severe (recorded			
Current abdominal discomfort	before examination)			
Loop reduction maneuvers	Number of times used, recorded by nurse assistant			
Position change	Start with left lateral, change as needed to supine, right lateral, prone.			
Abdominal compression	0=no, 1=Yes (sigmoid, transverse, hepatic, right side)			
Need to change technique	0=no, 1=yes (to air insufflation)			
Water volumes (insertion) Volume of water (infused and suctioned) upon arrival to the cecum, eq				
	volumes confirm appropriate application of water exchange			
Water volumes (total)	Volume of water (infused and suctioned) at the end of colonoscopy			
	Documented during withdrawal (4=excellent, no residual stool; 3=good, small			

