ADR, adenoma detection rate; SD, standard deviation; U, units. *90% power, 95% confidence or 5% α error level.					

male Veterans (e.g. proportion with no pain, insertion time, proximal colon ADR). The remaining previously listed secondary outcomes in male Veterans will be dropped (e.g. recalled pain, successful cecal intubation, overall and right colon ADR, willing to repeat).

Updated female Veteran sample size. After receipt of the critique, the PI identified 9 scheduled unsedated female Veterans (5 WE, 4 WECAC). RTMIP were WE, 6.2 (3.5) and WECAC, 3.5 (3.7). The reduction (44%) was 2.7/3.7 or 0.7 SD unit. The female Veterans had significantly higher RTMIP than the male Veterans when examined by WE, but the percent reduction of RTMIP by WECAC was equivalent (44%). The sample size/group needed to detect a difference at a level of significance of 0.0492 (adjusted for Obrien-Fleming interim stopping rules, one interim analysis at 50% completion) with 90% power is 43 or 86 total using a two-sided two sample t-test. Assuming 90% of subjects will be evaluable, we plan to recruit 96 female Veterans. Sample size of 96 will be sufficient to show significance in differences in some of the previously listed secondary outcomes related to quality colonoscopy in female Veterans (e.g. proportion with no pain, insertion time, overall and segmental ADR). The remaining previously listed secondary outcomes in female Veterans will be dropped (e.g. recalled pain, successful cecal intubation, willing to repeat).

Secondary outcome power estimates based pilot data in WE (n=5) and WECAC (n=4) in female Veterans					
Secondary Outcomes	Pilot (WE vs. WECAC)	Difference (SDU or %)	Sample size per group needed*		
Recalled pain, score (SD)	3.1(3) vs. 1.6(3)	1.5 (0.5 SDU)	84 (Will be dropped)		
Successful cecal Intubation	100% vs. 100%	0%	(Will be dropped)		
Proportion with no pain	0% vs. 25%	25%	32		
Insertion time, minutes (SD)	17(4.5) vs. 14(4.5)	-3 (0.7 SDU)	43		
Overall ADR - entire colon	20% vs. 50%	30%	48		
Proximal colon ADR	20% vs. 50%	30%	48		
Right colon ADR	20% vs. 50%	30%	48		
Willing to repeat, score (SD)	9.2(1.1) vs. 9.5(1.0)	0.3 (0.3 SDU)	233 (Will be dropped)		
ADR, adenoma detection rate; SD, standard deviation; U, units. *90% power, 95% confidence or 5% $\alpha$ error level.					

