Exploratory hypotheses. Co-variables affect patients' report of RTMIP. Patient-related factors include age, gender, ethnicity, education, BMI, indication for colonoscopy, current symptomatic hemorrhoids,

Dependent Variables	Variable	Analysis method		
Primary Outcome				
RTMIP	Continuous	Mixed effects regression, predict lower insertion pain, predictors-covariables		
Co-variables			Variable	Analysis method
Recalled maximum inse	Recalled maximum insertion pain score (blinded) [validates primary]			Correlate RTMIP
Body mass index (yes, no)			Continuous	
Age (<40 years) (yes, no); gender (male, female); ethnicity (White, Black, Hispanic, Asian, other) (yes, no); indication (Screening, surveillance, diagnostic); hemorrhoids (yes, no); chronic pain treatments (yes, no); substance abuse (yes, no); prior abdominal surgery (yes, no), sedation colonoscopy (yes, no), unsedated colonoscopy (yes, no), painful colonoscopy (yes, no); diverticulitis (yes, no); indication (abdominal pain) (yes, no); anticipation of pain (yes, no);  Exploratory variables			Binary	
Staff satisfaction (0=not satisfied to 10=very satisfied)			Continuous	
Adequacy of patient blinding (yes, no); Loop reduction maneuvers (yes, no); Position change (yes, no); Abdominal compression (yes, no); Need to change technique (yes, no); Failed (poor prep) (yes, no); Pain tolerance (patient reported) (0=low, 1=high); Reason for unsedated (no ride, personal preference, other) (yes, no); Previous endoscopy experience (0=not good, 1=good); Objective anxiety (0=none, 1=high) (by endoscopist before examination); overall adenoma detection - entire colon (yes, no);			Binary	

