chronic pain treatment, substance abuse, prior abdominal surgery, prior colonoscopy with or without sedation, current abdominal discomfort, expectation on day of colonoscopy, patient reported pain tolerance and subjective anxiety, objective anxiety assessed by colonoscopist, and reason for choice of no sedation. Procedure-related factors include technique of insertion, use of loop reduction maneuvers by the colonoscopist, change of patient position, application of abdominal compression by the assistant and insertion time, and length of colonoscope needed to reach the cecum. Examples: patients are more likely to report higher RTMIP amongst those with younger age, longer duration of insertion, lower expectation of painless insertion, female gender, low BMI, more frequent need for position change or abdominal compression. More patients will report lower RTMIP if there is low patient anxiety, good expectation of today's examination, no

prior abdominal surgery, colonoscopist use loop reduction maneuvers. The analysis of the exploratory outcomes will follow the same structure as the primary and secondary outcomes. To control for the multiplicity of exploratory outcomes we use the false-discovery rate (FDR) of Benjamini and Hochberg (67) rather than the traditional Bonferroni adjustment. The FDR assesses estimates the proportion of significant findings that are false positive results. The FDR method is less conservative and better preserves our ability to detect differences between groups.

Interim analysis. After 50% of subjects complete the protocol and data collection we will perform an inferential analysis of the primary endpoint as described in the statistical methods section. The only difference between the interim analysis of the primary endpoint and the final analysis will be the level of significance of the tests. If there is a significant treatment effect, this would communicated to the study Data and Safety Monitoring Board (DSMB) to consider early termination for efficacy.

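### Recalled pain, the only insertion-pain score given to a blinded observer, has no planned between-arm comparison, and its correlation with RTMIP hardly responds to unblinded recording bias

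*SAP*

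**What the plan says.** The Protocol's primary outcome table has RTMIP reported to the unblinded assisting nurse on a 0–10 scale and adds: "Timing of data collection will be at the discretion of the nurse to minimize bias by colonoscopist behavior". SAP, Potential problems, item 7, accepts that neither colonoscopist nor nurse can be blinded. It relies on earlier validation and on a coded video review that covers findings, cecal intubation and insertion time, not pain.

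Recalled pain is defined in Protocol Table 10: "Maximum pain during insertion reported to a blinded observer after" the procedure, before discharge. Protocol Table 11 and the SAP's exploratory table give it a validating role; the SAP row reads "Recalled maximum insertion pain score (blinded) [validates primary", and the method beside it is correlation with RTMIP. The Protocol's primary outcome table and Table 10 name the same method.

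As a between-arm outcome it is removed in both sexes. For men: "The remaining previously listed secondary outcomes in male Veterans will be dropped (e.g. recalled pain, successful cecal intubation". For women: "The remaining previously listed secondary outcomes in female Veterans will be dropped (e.g. recalled pain, successful cecal intubation, willing to repeat". Three other SAP statements come close to a comparison:

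- The text after the female table keeps the dropped variables on record to show that the groups are comparable, and foresees combined-sex differences, with adenoma detection as its example.
- Primary hypothesis fits RTMIP on group, gender and each covariate in Tables 9 and 10, with a covariate-by-group interaction. Table 10 includes recalled pain.
- Exploratory hypotheses says: "The analysis of the exploratory outcomes will follow the same structure as the primary and secondary outcomes".

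**The concern.** A correlation shows whether patients who score high on one scale also score high on the other. It says little about whether one arm's RTMIP scores are displaced. If an unblinded nurse asks at quieter moments, or records lower values, when the cap is fitted, RTMIP falls in WECAC while the ranking of patients within each arm stays nearly the same. The named validation would then look much as it would under a real effect.

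The score collected by a blinded observer bears on that question through its difference between arms, and the plan does not commit to reporting that difference. A positive RTMIP result would therefore reach readers without a pre-specified, observer-blinded comparison of the arms beside it.

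**Working it through.** **Inputs.** From the SAP sample-size sections: RTMIP 2.7 vs 1.5 in men (SD 2.2 and 2.1) and 6.2 vs 3.5 in women (SD 3.5 and 3.7); recalled pain 1.5 vs 0.5 (SD 2) in men and 3.1 vs 1.6 (SD 3) in women; 72 men and 43 women evaluable per arm. The documents give no value for the within-arm correlation of the two scores, so 0.5 to 0.9 is assumed, with 0.7 as base case.

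**1. The plan's own figure.** For 0.5 SD, 90% power and two-sided 5%, n per group = 2(1.960 + 1.282)²/0.5² = 84.1, against 84 stated. The exact t-test gives 85.03, so 86. The figure is reproduced to within 2. It exceeds the recruited numbers per group in each sex alone (160/2 = 80 and 96/2 = 48). Power with the evaluable numbers is 85% in men and 63% in women.

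**2. Sexes combined.** There are 72 + 43 = 115 per arm.
- Difference: (72×1.0 + 43×1.5)/115 = 1.19.
- Within-sex SD: √[(72×4 + 43×9)/115] = 2.42, so d = 0.49.
- SE: 2.42×√(2/115) = 0.32, so the 95% CI half-width is 0.63.
- Power: 96% for the pilot effect, 86% at 0.4 SD, 62% at 0.3 SD.

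**3. Why the correlation hardly moves.** In one sex with 1:1 allocation, within-arm correlation ρ, SDs sR and sQ, and arm differences dR (RTMIP) and dQ (recalled):

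r = (ρ·sR·sQ + dR·dQ/4) / √[(sR² + dR²/4)(sQ² + dQ²/4)]

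Men, ρ = 0.7, sR = 2.2, sQ = 2, dR = 1.2:
- All recording bias (dQ = 0): 3.08/√(5.20×4.00) = 0.675.
- All real (dQ = 1): 3.38/√(5.20×4.25) = 0.719.

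With no real effect, a 1.2-point shift alone makes the male RTMIP test significant at 0.0492 with probability 90%; a 0.6-point shift does so with probability 37%.

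**4. Both sexes, simulated.** 4000 runs per scenario, 115 per arm, RTMIP SD 2.15 in men and 3.6 in women. The RTMIP difference stays at its pilot value, and the recalled difference shrinks by the fraction that is bias. Within-arm correlation 0.7:

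| | All real | Half bias | All bias |
|---|---|---|---|
| Correlation, RTMIP with recalled | 0.74 (0.67–0.80) | 0.72 | 0.70 (0.62–0.77) |
| Recalled difference, WECAC − WE | −1.19 | −0.60 | 0.00 |
| Recalled difference significant | 96% | 46% | 5% |
| Group coefficient, RTMIP on group, sex, recalled | −0.80 | −1.28 | −1.75 |

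At within-arm 0.5 and 0.9 the correlation again differs by only about 0.04 between the extremes (0.575 vs 0.535; 0.899 vs 0.863). With scores clipped to 0–10, the recalled difference is significant in 93%, 42% and 6% of runs.

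**5. The covariate model.** Distance between all real and all bias, in standard errors: direct recalled-pain contrast about 3.7 (1.19/0.32) whatever the correlation; model group coefficient 2.1, 3.6 and 7.5 at within-arm 0.5, 0.7 and 0.9. The coefficient needs the correlation to be read: all real at 0.5 gives −1.07, and half bias at 0.9 gives −1.15. With the SAP's interaction term and recalled pain uncentred, the group term is significant in 62% of all-real runs, against 83% without the term or with recalled pain centred.

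**6. Interim.** At 36 men and 21–22 women per arm, RTMIP reaches p < 0.0054 in about 53–60% of runs under the pilot effect. With 57 per arm, the recalled-pain half-width is 0.90 and power 74%.

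**The case against.** The strongest reply is that the covariate model already does much of this work. Recalled pain is in Table 10, the correlation needed to read the group coefficient is planned, and at a within-arm correlation of 0.7 the model separates the extremes about as well as the direct contrast (better at 0.9, worse at 0.5). That stands. What is missing is that the SAP never presents the coefficient as a bias check or says how to read it. Likewise, the text on comparability and the general reference to two-sample tests make a by-arm summary of recalled pain plausible, but not a commitment.

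Several stronger inferences are tempting, and the documents do not support them:

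- *RTMIP is the wrong primary outcome.* The Protocol gives its reason: "The primary outcome of RTMIP (unblinded measure, but one on which clinical decision is made) will be compared".
- *The primary outcome has no protection against bias.* The patient supplies the score with eyes covered, a guess test checks the masking, and nurse-chosen timing is itself offered as a safeguard against colonoscopist influence. The open path is the nurse's timing, prompting and recording. The documents give no size for such bias; the half and all cases are illustrations.
- *A smaller recalled difference would prove bias.* Protocol, Work Accomplished (e), reports that "RTMIP (unblinded) is uniformly higher than recalled maximum insertion pain (blinded) and the 2 measures are significantly correlated", so some shrinkage is expected. Recall is also given after withdrawal, when the patient may watch and may have seen the cap. And prompting that alters the patient's own rating may alter recall too, which the contrast would miss.
- *The trial will stop at the interim if significant.* SAP Hypotheses Testing says so, but SAP Interim analysis refers the result to the DSMB for consideration. The two passages need reconciling.

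**Conclusion.** The concern holds in this limited form. The only named validation of an openly recorded primary outcome differs by about 0.04 between an effect that is all real and one that is all recording bias, with overlapping sampling ranges. The recalled-pain difference between arms separates those extremes clearly (96% vs 5% significant) but will often leave partial bias unresolved (46%).

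This rests on the pilot inputs (only nine women), an assumed within-arm correlation of 0.5 to 0.9, and bias that acts on timing or recording without altering later recall. The low sensitivity of the correlation holds across that range. The recommendation is a worthwhile, low-cost strengthening of the SAP; the point does not invalidate the primary analysis.

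**What to change.** Pre-specify in the SAP the WECAC-minus-WE difference in recalled maximum insertion pain with its 95% CI, sexes combined and adjusted for sex, as a supportive analysis. Report it beside the RTMIP difference and judge it by size and CI, not by its p-value.

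State the limits with it: it addresses timing and recording but not prompting that also changes recall; recalled pain runs lower than RTMIP and follows withdrawal, so only the observer is reliably blinded; partial bias may stay unresolved; and precision falls if the trial ends at the interim.

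If the covariate model containing recalled pain is also meant as a bias check, say so, and report its group coefficient with CI (recalled pain centred if the interaction is kept) together with the within-arm correlation.

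The cost is SAP wording and one extra supportive comparison. The data are already collected, and no alpha is taken from the primary test.

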Updated male Veteran sample size. Pilot data in scheduled unsedated male Veterans were updated. The real time maximum insertion pain (RTMIP) [mean (SD)] was 2.7 (2.2) with WE (n=87) and 1.5 (2.1) with WECAC (n=38). The reduction (44%) 2.7-1.5=1.2 is 1.2/2.2=0.55 standard deviation (SD) units. The sample size/group needed to detect a difference at a level of significance of 0.0492 (adjusted for Obrien-Fleming interim stopping rules, one interim analysis at 50% completion) with 90% power is 72 or 144 total using a twosided two sample t-test. Assuming 90% of subjects will be evaluable, we plan to recruit 160 male Veterans. Updated pilot data showed the PI performed 30 scheduled unsedated colonoscopies (male) in 1 year when ~2200 colonoscopies were offered at VAGLAHS (1.36%). At participating sites, a total of ~9000 colonoscopies (VAGLAHS 2200, VANCHCS 3300, VAPAHCS 3500) will be performed each year. For purpose of conservative estimation, 1/2 of 1.36% (0.68%) of all colonoscopies will be presumed to be in scheduled unsedated male Veterans when the option is made available up front. In 51 month (4.25 year) enrollment period, a total of 38250 colonoscopies will be performed. 260 (0.68% of 38250) male Veterans will receive scheduled unsedated colonoscopy, making target enrollment of 160 achievable (only 160/260 = 62% enrollment rate needed). In support of this possibility, in two prior RCT in scheduled unsedated male Veterans at VAGLAHS and VANCHCS comparing WE vs. air colonoscopy, high enrollment rates of 97.7% (84/86) and 95.2% (100/105), respectively, were recorded. Sample size of 160 will be sufficient to show significant differences in some of the previously listed secondary outcomes related to quality colonoscopy in

Secondary outcome power estimates based pilot data in WE (n=87) and WECAC (n=38) in male Veterans					
Secondary Outcomes	Pilot (WE vs. WECAC)	Difference (SDU or %)	Sample size per group needed*		
Recalled pain, score (SD)	1.5(2) vs. 0.5(2)	1 (0.5 SDU)	84 (Will be dropped)		
Successful cecal Intubation	98% vs. 100%	2%	(Will be dropped)		
Proportion with no pain	18% vs. 46%	28%	54		
Insertion time, minutes (SD)	15(5) vs. 12( 5)	-3 (0.6 SDU)	58		
Overall ADR - entire colon	36% vs. 50%	14%	258		
Proximal colon ADR	17% vs. 40%	23%	76		
Right colon ADR	20% vs. 40%	20%	106		
Willing to repeat, score (SD)	9.0(2.5) vs. 9.6(0.9)	0.6 (0.4 SDU)	(Will be dropped)		

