Primary hypothesis. Real-time maximum insertion pain (RTMIP) is significantly lower in the patients examined by the WECAC technique compared with the WE technique. The analysis will compare 2 groups (WECAC vs. WE) with a two sample t-test. If the data show substantial non-normality (as in a prior dataset with WE (5)); we will compare the groups with a Mann-Whitney *U* test; P<0.0492 considered significant. Secondary analysis of the primary outcome will utilize mixed effects regression models to evaluate the effects of potential covariates/confounds described in Tables 9 and 10. First, we will assess the effect of each individual covariate in regression models including the effect for group assignment and gender (stratification factor in the randomization), as well as the covariate by group interaction. Next, we will construct a multiple regression model with the set of covariates found to be significant (either as a main effect or an interaction effect) in an overall regression model along with group assignment.

Dependent Variables	Variable Type	Analysis method
Primary Outcome		
RTMIP (0=none,	Continuous	2 sample Student t test. However, if distribution of the data is skewed as
10=most severe)	Continuous	seen in an earlier study (5), the Mann-Whitney U test will be used.

We have updated the analytic plan to include multi-level random effects (hierarchical model) for study site and provider within site. We will include two levels of random effects in this model: 1. random effects for study site, 2. random effects for provider which will be nested within sites.

Secondary hypotheses. WECAC produces significantly higher quality colonoscopy outcomes. For example, when WE alone and WECAC are compared, the proportion completing colonoscopy with no pain, insertion time, and ADR in the proximal colon will be significantly different. For continuous secondary outcomes (e.g. insertion time), we will use a similar analysis strategy as that used for the primary outcome. For dichotomous secondary outcomes (e.g., no pain, proximal colon ADR) we will use Chi-square tests to compare the outcomes between the groups. Generalized logistic models will be used to adjust for covariates, gender and study site for these outcomes.

Dependent Variables	Variable Type	Analysis method
Insertion time	Continuous	Student t test
No insertion pain (yes, no); proximal colon adenoma detection (yes, no)	Binary	Chi square

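### Female insertion time is sized on an effect rounded up from 0.67 to 0.7 SD, and the ADR needs match the recruited rather than the evaluable numbers, so 90% power is slightly overstated for three secondary outcomes

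*SAP*

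**What the plan says.** The two sample-size paragraphs of the SAP (updated male and updated female Veteran sample size) first size the primary pain outcome. For women this comes out "with 90% power is 43 or 86 total using a two-sided two sample t-test", and the next step is "Assuming 90% of subjects will be evaluable, we plan to recruit 96 female Veterans". For men it comes out "with 90% power is 72 or 144 total using a twosided two sample t-test", raised to 160 on the same 90% assumption.

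Each paragraph has a table of secondary outcomes, footnoted "90% power, 95% confidence or 5% α error level". The entries that matter here are:

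- Female insertion time: mean (SD) minutes of "17(4.5) vs. 14(4.5"), shown as 0.7 SD units, 43 per group.
- Female overall, proximal and right colon ADR: 20% vs 50%, 48 per group for each.
- Male proximal colon ADR: 17% vs 40%, 76 per group.

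From the female table the SAP concludes: "Sample size of 96 will be sufficient to show significance in differences in some of the previously listed secondary outcomes related to quality colonoscopy". It names the outcomes meant: "female Veterans (e.g. proportion with no pain, insertion time, overall and segmental ADR"). The male paragraph makes the same claim for 160 men, naming no pain, insertion time and proximal colon ADR.

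For the analysis, the Statistical Analysis paragraph includes all randomized patients. Secondary hypotheses assigns a Student t-test to insertion time, and for binary outcomes "we will use Chi-square tests to compare the outcomes between the groups".

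**The concern.** Two things do not fit together. First, a difference of 3 minutes with an SD of 4.5 is not 0.7 SD, and rounding an effect upward lowers the number that appears to be needed. Second, both paragraphs allow for a 10% loss when sizing the primary outcome, but the secondary needs of 48 and 76 per group can be met only if that loss is ignored.

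The SAP uses these tables as its reason for keeping some secondary outcomes and dropping others. Insertion time and proximal colon ADR are two of the three secondary outcomes listed in the Protocol. If one of them narrowly misses significance, readers will interpret that result against the power the plan claimed.

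**Working it through.** **Inputs.** Two-sided alpha 0.05 and 90% power (table footnote; two-sided is assumed, as for the primary outcome). Then (1.960 + 1.2816)² = 10.507. Pilot values are those listed above.

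**Numbers per group.** Recruited: 96/2 = 48 women and 160/2 = 80 men. Evaluable at 90%: 0.9 × 48 = 43.2, i.e. 43 women (the plan's own figure), and 0.9 × 80 = 72 men.

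**Reproducing the plan's entries.**

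- Means, normal approximation, n = 2 × 10.507/d². At d = 0.7: 21.015/0.49 = 42.9, so 43. This matches.
- Proportions, unpooled variance, n = 10.507 × [p₁(1−p₁) + p₂(1−p₂)]/(p₁−p₂)².
  - Female ADR: 10.507 × (0.16 + 0.25)/0.09 = 47.9, so 48. This matches.
  - Male proximal ADR: 10.507 × (0.1411 + 0.24)/0.0529 = 75.7, so 76. This matches.

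**Female insertion time with the unrounded effect.** d = 3/4.5 = 0.667. The normal approximation gives 21.015/0.4444 = 47.3, so 48. The t-test (noncentral t) gives 48.3, so 49. At d = 0.7 the t-test would need 44, so the rounding accounts for five of the six extra patients per group and the normal approximation for one.

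**Power at the two possible denominators.** Noncentral t for insertion time; exact binomial power of the uncorrected chi-square test for ADR.

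| Outcome | Listed need | Evaluable n | Power | Randomized n | Power |
|---|---|---|---|---|---|
| Female insertion time (0.667 SD) | 43 | 43 | 86.3% | 48 | 89.8% |
| Female ADR, 20% vs 50% | 48 | 43 | 85.5% | 48 | 88.5% |
| Male proximal ADR, 17% vs 40% | 76 | 72 | 87.9% | 80 | 91.0% |

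By the plan's own unpooled formula the ADR figures are 86.7% (43 women) and 88.5% (72 men), rising to 90.1% (48 women) and 91.5% (80 men).

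**Outcomes that are not short.** At the evaluable numbers, power is 99.8% for female no-pain (0% vs 25%, 43 per group), 95.8% for male no-pain (18% vs 46%, 72 per group) and 94.7% for male insertion time (0.6 SD, 72 per group). All three are higher still with every randomized patient.

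**The case against.** The strongest reply is that the 90%-evaluable figure belongs to the primary calculation. The sufficiency sentences refer to 96 and 160 recruited, and the SAP analyses everyone randomized. On that reading 48 ≤ 48 and 76 ≤ 80, and the tables fit the sample. This largely disposes of the male point. It does not fully dispose of the female ones: with all 48 women per group, the planned tests still give 89.8% and 88.5%. Full inclusion is also uncertain for insertion time. The SAP's rule for early discontinuation supplies a pain score, whereas the Protocol defines insertion time as time to cecum, and neither document gives a value when the cecum is not reached.

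A second reply is that the SAP claims sufficiency only for some outcomes. That stands against any general charge, but the sentence goes on to name insertion time and ADR.

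A third is that the unpooled formula is a standard approximation. That is correct. A reader might infer that every binary entry is wrong because a chi-square test is planned. The documents do not support this: for female no-pain, the listed 32 per group already has 97.5% exact chi-square power, so raising it would make the table less accurate.

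A fourth is that no decision changes. That also stands. The needs listed for outcomes dropped on size (84 and 233 in women; 84, 106 and 258 in men) remain far above the sample.

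Finally, the female inputs come from 5 and 4 patients; 20% vs 50% is 1/5 vs 2/4. That uncertainty dwarfs a few points of power. It puts the correction in proportion, but it is also a reason not to assert sufficiency.

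**Conclusion.** The point holds for three entries. Female insertion time is a plain arithmetic error: 0.67 SD was entered as 0.7 SD, so the listed 43 per group gives about 86% power and 49 are needed. Female ADR and male proximal ADR are stated against a denominator that the same paragraphs do not expect to be evaluable. At the evaluable numbers they have about 85% and 88%.

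The shortfall from 90% is about 4 to 5 percentage points in women and 2 in men. If all randomized patients contribute data, it shrinks to almost nothing for female insertion time and about 1.5 points for female ADR, and disappears for male proximal ADR. These figures take the pilot effects at face value and assume equal groups and two-sided alpha 0.05.

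A reader might infer that the 90% power fails for the secondary outcomes generally, or that the trial is too small. Neither follows. No-pain in both sexes and male insertion time exceed 90% under either denominator, and the primary pain sample size does not depend on these entries.

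**What to change.** In the female secondary-outcome table, change insertion time to 0.67 SD and 49 per group. For the three affected outcomes, replace the statement that the sample will be sufficient with the power under each denominator:

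- Female insertion time: about 86% at 43 evaluable per group; about 90% if all 48 are analysed.
- Female ADR: about 85% at 43; about 88% at 48.
- Male proximal colon ADR: about 88% at 72; about 91% at 80.

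Say which number each secondary analysis is expected to use, and note beside the female table that its inputs come from 9 pilot patients. Leave the no-pain entries as they are and add no patients.

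The cost is one table entry and a few sentences. The stated power becomes slightly less favourable; recruitment, the choice of outcomes and the analyses are unchanged.
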